#### **6.1.2. Supplementary/Sensitivity Analyses**

##### **6.1.2.1. Supplementary Analyses**

###### Supplementary Analysis 1

- Estimand strategy: hypothetical ([Section 2.3.3](#)).
- Analysis set: DBFAS ([Section 4.1.1](#))
- Analysis methodology: methods described in Section 5.2.1.
- Censoring time and risk period: On-Treatment Censoring Time and Risk Period ([Section 5.3.1.1](#)).
- Intercurrent events and missing data: See definitions described in Section 2.3.3 for intercurrent events; and Section 5.3.1 for missing values.

###### Supplementary Analysis 2

- Estimand strategy: treatment policy ([Section 2.3.3](#)).
- Analysis set: DBFAS ([Section 4.1.1](#))

- Analysis methodology: methods described in [Section 5.2.1](#).
- Censoring time and risk period: On-Study Censoring Time and Risk Period ([Section 5.3.1.1](#)).
- Intercurrent events and missing data: See definitions described in [Section 2.3.3](#) for intercurrent events; and [Section 5.3.1](#) for missing values.

Supplementary Analysis 2 will include observations that occur after the intercurrent event of investigational product discontinuation. Subjects discontinuing investigational product in the double-blind phase, for reasons other than flare, before reaching 52 weeks of double-blind treatment will continue to be followed up for flares either via scheduled study visits in this study or in the LTE study A3921145 (for subjects who withdraw from this study and roll over) for up to 52 weeks post randomization. For data coming from A3921145 study, disease flare will be programmatically evaluated using the same approach by CCC as in this study. Flares occurring after investigational product discontinuation in A3921165 study come from either the CCC flare assessment at regularly scheduled study visits or the follow-up visit post investigational product discontinuation.

### **6.1.2.2. Sensitivity Analyses: Tipping Point Analysis**

#### Sensitivity Analysis 1

This analysis will be performed only when superiority is achieved based on the primary analysis for the primary endpoint ([Section 6.1.1](#)).

The impact of missing data (ie, censoring) on the primary analysis (composite estimand) will be evaluated through model-based multiple imputation. For subjects who are censored under the composite estimand, the imputation will be done to the LSLV of Study A3921165. Imputation model will be fit for patients assigned to tofacitinib and placebo.

Tipping point analysis will be conducted to explore the plausibility of missing data assumptions under which the conclusions change, i.e., under which there is no longer evidence of a treatment effect. The tipping point analysis will be two-dimensional, i.e., will allow assumptions about the censored times on the two arms to vary independently.

In the tipping point analysis approach, the post-censoring hazard of flares for subjects with censored time to flare will be varied over a grid of sensitivity parameters that increase or decrease the hazard function relative to the CAR (censoring at random) analysis in both the tofacitinib and placebo groups.

The primary endpoint is time to disease flare in the double-blind phase. Patients who are censored without disease flare contribute partial information about the endpoint, which can be analyzed using standard statistical methods for survival data. Weibull regression model will be fit for both observed and censored data as the imputation model. Statistical simulations were conducted suggesting estimation bias for Weibull parameters was minimal when the Weibull shape parameter was  $\geq 1$ . The assumed Weibull shape parameter of 1 was supported by data of a prior completed pJIA study (A3921104). Conditional on the observed

censored time, a time-to-flare will be imputed, subject to the end-of-study constraint as follows: use the imputed time-to-flare if the imputed time-to-flare is prior to the end of study (ie, LSLV of Study A3921165); but censored at the end of the study, if the imputed time-to-flare exceeds the LSLV date of Study A3921165.

The completed imputed data sets will be analyzed using the same approach as the primary analysis (ie, unstratified log-rank test) in [Section 5.2.1](#). This will be repeated for R times per each scenario. The multiple imputation analysis will be applied to each set of the two sensitivity parameters in the two-dimensional tipping point analysis.

More detailed descriptions are provided in [Appendix 5](#).

### Sensitivity Analysis 2

This analysis will be performed only when superiority is achieved based on the primary analysis for the primary endpoint ([Section 6.1.1](#)) and the result of Supplementary Analysis 2 ([Section 6.1.2.1](#)) is consistent with the primary analysis.

The impact of missing data (ie, censoring) on Supplementary Analysis 2 (treatment policy estimand, [Section 6.1.2.1](#)) will be evaluated through model-based multiple imputation. For subjects who are censored under the treatment policy estimand and not enrolled in the LTE study (Study A3921145), the imputation will be done to the LSLV of Study A3921165. For subjects who are censored under the treatment policy estimand and enrolled in the LTE study (Study A3921145), the imputation will be done to the LSLV of Study A3921165 or to Randomization Day + 378 (the upper limit of the DB Week 52 visit window), whichever comes later. Imputation model will be fit for patients assigned to tofacitinib and placebo.

Weibull regression model will be fit for both observed and censored data as the imputation model. Conditional on the observed censored time, a time-to-flare will be imputed, subject to the constraint as follows: use the imputed time-to-flare if the imputed time-to-flare is within the risk period for imputation defined above; but censored at the end of the risk period for imputation, if the imputed time-to-flare exceeds the risk period for imputation.

A tipping point analysis similar to Sensitivity Analysis 1 will be conducted to explore the plausibility of missing data assumptions under which the conclusions change, i.e., under which there is no longer evidence of a treatment effect.

More detailed descriptions are provided in [Appendix 5](#).

## **6.2. Secondary Endpoints**

The secondary endpoints will be analyzed in the open-label phase and by treatment group in the double-blind phase. For further information on the treatment groups please refer to [Section 5.2.4](#) and [Section 5.2.5](#). For missing data handling of the secondary endpoints, please refer to [Section 5.3](#).

### 6.2.1. Secondary Endpoints Analysis – Double-Blind Withdrawal Phase

The double-blind secondary endpoint analyses will be carried out using the DBFAS population, by treatment group (tofacitinib and placebo).

#### 6.2.1.1. Binary Secondary Endpoints in Double-Blind Phase

Except the endpoint of occurrence of disease flare by visit, which is estimated in the analyses of the primary endpoint (Section 6.1.1 and Section 6.1.2.1), all other DB binary secondary endpoints listed in Section 3.2.1 (aJIA ACR 30/50/70/90/100 response, absence of fever, occurrence of inactive disease and minimal disease activity, occurrence of JIA ACR inactive disease and clinical remission), are analyzed as below:

- Estimand strategy: Composite (Section 2.3.2.1).
- Analysis set: DBFAS (Section 4.1.1).
- Analysis methodology: Descriptive summary in Section 5.2 and analysis methods in Section 5.2.2 will be followed.
- Intercurrent events and missing data: See definitions described in Section 2.3.2.1 for intercurrent events and Section 5.3.2 for missing data.
- The basic summary statistics will be calculated by visit. The normal-approximated 95% CI and 2-sided p-value for the treatment effect will be presented at each scheduled visit in the double-blind phase through Week 52.

#### 6.2.1.2. Continuous Secondary Endpoints in Double-Blind Phase

Change from open-label baseline in each sJIA ACR core variable, except for disability index from the CHAQ for which change from double-blind baseline will be considered, will be analyzed as below:

- Endpoints:
  - Change from OL baseline in number of joints with active arthritis
  - Change from OL baseline in number of joints with limited range of motion
  - Change from OL baseline in physician global evaluation of disease activity
  - Change from OL baseline in parent/legal guardian/subject evaluation of overall well-being [from the CHAQ]
  - Change from DB baseline in disability index from the CHAQ
  - Change from OL baseline in ESR
- Estimand strategy: Treatment policy (Section 2.3.2.2).

- Analysis set: DBFAS ([Section 4.1.1](#)).
- Analysis methodology: Descriptive summary in [Section 5.2](#) and analysis methods in [Section 5.2.3](#) will be followed.
- Intercurrent events and missing data: See definitions described in [Section 2.3.2.2](#) for intercurrent events and MMRM described in Section 5.2.3 for missing data.
- The basic summary statistics will be calculated by visit. The least-squares (LS) means, the 95% confidence interval for the LS means, the between treatment difference, the corresponding 95% confidence interval and 2-sided p-values for the main treatment effect will be presented for change from baseline value at each scheduled visit in the double-blind phase through Week 52.

Analysis details of other continuous secondary endpoints are provided in [Section 6.2.1.3](#).

#### **6.2.1.3. Supplementary Analyses**

For aJIA ACR 30/50/70/90/100 response at each scheduled visit in the double-blind phase through Week 52, an additional analysis using the treatment policy estimand strategy ([Section 2.3.4](#)) will be performed. It will use the same methodology and summary as in [Section 6.2.1.1](#) but will also include data collected after the intercurrent events of investigational product discontinuation, ie, all data collected while On- and Off-investigational product until Week 52 will be used to derive the endpoints.

For all DB continuous secondary endpoints listed in [Section 3.2.1](#) (change from DB baseline in JADAS-27 ESR/CRP, change from both OL and DB baseline in each sJIA ACR core variable, change from DB baseline in CHQ responses and CHAQ discomfort index), an analysis using the hypothetical estimand strategy (Section 2.3.4) will be performed. It will use the same methodology and summary as in [Section 6.2.1.2](#) but only the on-treatment data ([Appendix 3.13](#)) will be used.

#### **6.2.2. Secondary Endpoints Analysis – Open-Label Phase**

In general open-label analyses will be broken down by Part 1 and Part 2, and open-label overall, unless otherwise specified. There will be no treatment comparisons for the open-label analyses and missing data will not be imputed, unless otherwise specified for the calculation of specific endpoints. Summaries by visit will be done separately for Part 1 and Part 2, using the corresponding Part 1 or Part 2 open-label analysis sets (OLPT1 and OLPT2).

For below binary endpoints, descriptive summary statistics (number and percentage) mentioned in Section 5.2 will be presented. Percentages will be calculated out of the number of subjects with non-missing values at each visit.

- Successfully tapering at the end of Part 2 of the open-label phase and Achievement of corticosteroid dose of  $\leq 0.2$  mg/kg/day or 10 mg/day at the end of OL Part 2 phase

Analyses will be conducted using the OLPT2 analysis set.

- Adapted JIA ACR30/50/70/90/100 responses at each visit from Day 7 onward
- JADAS-27 Inactive Disease and Minimal Disease Activity at each visit
- Absence of Fever (lack of fever due to sJIA in the week preceding the assessment) at each visit
- JIA ACR Inactive Disease at each visit
- Occurrence of fever attributed to sJIA on Day 3, 7 and 14  
Summary will be for all the tofacitinib OLPT1 subjects.
- CRP  $\leq$  10 mg/L at every visit of the open-label phase

Descriptive statistics as described in [Section 5.2](#) will be tabulated for:

- JADAS-27 ESR and CRP scores and change from OL baseline values at each visit
- CHAQ responses and change from OL baseline values at each visit  
Details on the calculation of CHAQ responses can be found in [Appendix 3.9](#).
- CHQ responses and change from OL baseline values at the end/last visit of Part 1 and Part 2 of the open-label phase
- JIA ACR Core Set Variables and change from OL baseline values at each visit

Besides the descriptive summary mentioned in Section 5.2, Kaplan-Meier methods described in [Section 5.2.1](#) will be used to analyze below time-to-event endpoint:

- Time to Adapted JIA ACR30 Response in Part 1 of the open-label phase

Analysis will be done using the OLPT1. Subjects that do not achieve an adapted JIA ACR30 response in Part 1 (withdraw from the study) will be censored at their last available response assessment in Part 1. Time to response will be counted since the first dose of tofacitinib in the study for all the subjects.

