**Secondary:**

- To assess efficacy of tofacitinib versus placebo in sJIA patients at various time points in the double-blind randomized withdrawal phase, as measured by the following.
  - a. Percentage of subjects with sJIA disease flares
  - b. Percentage of subjects with Adapted JIA ACR 30/50/70/90/100 responses
  - c. Changes from baseline in Juvenile Arthritis Disease Activity Score (JADAS-27)
  - d. Percentage of subjects achieving inactive disease and clinical remission (JIA ACR)
  - e. Percentage of subjects with inactive disease and minimal disease activity (JADAS-27)
  - f. Other evaluations specified under “Efficacy endpoints” for the double-blind phase.
- To assess the efficacy of tofacitinib in sJIA subjects in the open-label treatment phase, as measured by:
  - a. Percentage of subjects with successful corticosteroids tapering per protocol at the end of the open-label phase in subjects with sJIA receiving corticosteroids at start of open-label phase
  - b. Percentage of subjects with Adapted JIA ACR 30/50/70/90/100 responses at every visit from Day 7 onward
  - c. Other evaluations specified under “Efficacy endpoints” for the open-label phase.
- To assess the safety and tolerability of tofacitinib in sJIA patients.
- To assess the pharmacokinetics of tofacitinib in sJIA subjects in the open-label phase.

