### 3.2.2. Open-Label Treatment Phase

- Achievement of corticosteroid tapering per protocol at the end of the open-label active treatment period in applicable subjects receiving corticosteroids on study Day 1 of the open-label phase.

A successfully tapered subject is one that has completed Part 2 of the OL by reaching their target corticosteroid dose and maintaining an adapted JIA ACR30 response for four weeks on this dose.

- Achievement of a corticosteroid dose of  $\leq 0.2$  mg/kg/day or 10 mg/day (whichever is lower) at the end of the open-label treatment period in subjects receiving corticosteroids on Day 1 of the open-label phase.
- Occurrence of CRP  $\leq 10$  mg/L at every visit of the open-label phase.
- Occurrence of fever (Temp  $>38$  Degrees Celsius) attributed to sJIA at Day 3, Day 7 and Day 14 of the open-label phase.
- Time from first tofacitinib dose to first adapted JIA ACR30 response in Part 1 of the open-label phase.
- Adapted JIA ACR 30/50/70/90/100 response at every visit from Day 7 onward in the open-label phase.
- “Absence of fever”, defined as absence of fever due to sJIA in the week preceding the assessment at every visit from Day 7 onward in the open-label phase.
- Change from OL baseline in Juvenile Arthritis Disease Activity Score (JADAS-27, calculated based the ESR and CRP inflammation biomarkers separately) at every visit from Day 7 onward in the open-label phase.
- Change from OL baseline in each JIA ACR core variable at every visit from Day 7 onward in the open-label phase.
- Occurrence of inactive disease status and minimal disease activity (JADAS-27, calculated based the ESR and CRP inflammation biomarkers separately) at every visit from Day 7 onward in the open-label phase.
- Occurrence of JIA ACR inactive disease status at every visit from Day 7 onward in the open-label phase.
- Change from OL baseline in Child Health Questionnaire (CHQ) responses at the end of Part 1 and Part 2 of the open-label phase.
- Change from OL baseline in Child Health Assessment Questionnaire (CHAQ) - Discomfort Index at every visit from Day 7 onward in the open-label phase.

For details of the derivation of the secondary endpoints, see [Appendix 3.1](#) to Appendix 3.9.

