#### 4.2.2. Open-Label Part 2 Analysis Set

Open-label part 2 (OLPT2) analysis set will consist of all subjects who were enrolled into the open-label part 2 phase of the study and received at least one dose of investigational product in part 2.

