**Table 4. Summary of Efficacy Analyses**

Endpoint	Estimand and Analysis Type	Population	Data Inclusion and Rules for Handling Intercurrent Events and Missing Data	Analysis Model
sJIA ACR core set variables change from DB baseline by DB visit 

• number of joints with active arthritis

• number of joints with limited range of motion

• physician global evaluation of disease activity

• parent/legal guardian/subject evaluation of overall well-being (from the CHAQ)

• CHAQ disability index

• ESR

	Estimand 7 Hypothetical Strategy  Secondary analysis	DBFAS	Only data collected On-investigational product are included.  Missing data are not imputed and handled using MMRM.	MMRM with terms treatment, visit, treatment*visit, DB baseline, DB baseline*visit
CHAQ disability index change from DB baseline by DB visit	Secondary estimand  Estimand 3 Treatment Policy Strategy  Secondary analysis	DBFAS	All data collected On- and Off-investigational product are included.  Missing data are not imputed and handled using MMRM.	MMRM with terms treatment, visit, treatment*visit, DB baseline, DB baseline*visit
Steroid taper success in OL Part 2	Summary	OLPT2	Only use observed data	N/A
Steroid reduction to $\leq 0.2$ mg/kg/day or 10 mg/day in OL Part 2	Summary	OLPT2	Only use observed data	N/A
Adapted JIA ACR responses by OL Part 1 / 2 visit	Summary	OLPT1 / OLPT2	Only use observed data	N/A
JADAS-27 inactive disease CRP by OL Part 1 / 2 visit	Summary	OLPT1 / OLPT2	Only use observed data	N/A

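### The ≤0.2 mg/kg/day corticosteroid endpoint is defined in children on corticosteroids at Day 1 but computed in those who entered Part 2; the taper endpoint only needs its word *applicable* defined

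*SAP*

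**What the plan says.** **Endpoint definitions.** SAP 3.2.2, matching Protocol 2.2.2, places the dose endpoint "at the end of the open-label treatment period in subjects receiving corticosteroids on Day 1 of the open-label phase". The companion taper endpoint is stated "in applicable subjects receiving corticosteroids on study Day 1 of the open-label phase". For the latter the SAP adds: "A successfully tapered subject is one that has completed Part 2 of the OL by reaching their target corticosteroid dose", together with an adapted JIA ACR30 response held for four weeks on that dose. The open-label objective on tapering (SAP 2.1, Protocol 2.1.2) is framed "in subjects with sJIA receiving corticosteroids at start of open-label phase".

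**Analysis instructions.** SAP 6.2.2 treats both endpoints in one bullet. It assesses the dose endpoint "at the end of OL Part 2 phase" and then states "Analyses will be conducted using the OLPT2 analysis set". Appendix 1, Table 4 repeats this: the row "Steroid taper success in OL Part 2" and the dose row after it both show population OLPT2 and observed data only. SAP 4.2.2 defines OLPT2 as those "who were enrolled into the open-label part 2 phase of the study and received at least one dose of investigational product in part 2". It sets no corticosteroid condition.

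**Who reaches Part 2.**
- Protocol 3.2.1 discontinues children who, for example, do not achieve or hold the required response in Part 1.
- Protocol 3.2.2 lets children stable at ≤0.2 mg/kg/day who hold response go straight to randomization.
- Protocol 3.2.1, however, describes children on no corticosteroid, or not required to taper, as proceeding to Part 2.
- SAP 6.5 plans a count of children randomized directly after Part 1, so the SAP expects some to bypass Part 2.

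**The concern.** The dose endpoint carries no qualifier: it covers every child on corticosteroids at Day 1, at the end of that child's open-label treatment. The analysis set is fixed later in the trial, by entry to Part 2. A child who skips Part 2 has no end-of-Part-2 dose, so the plan as written cannot classify that child. A child discontinued in Part 1 disappears from the denominator. A child never on corticosteroids may be counted if enrolled in Part 2.

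The reported percentage would thus appear under an endpoint name that promises a different population. A reader could not repair it from the other planned output: the disposition counts in SAP 6.5 are not planned by corticosteroid use, and SAP 6.4 rules out subgroup analyses of open-label endpoints.

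**Working it through.** The plan states no rate for either endpoint, so there is no figure to reproduce. The check compares the two denominators.

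**Day-1 corticosteroid users, by route**

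| Child | In the defined population? | In OLPT2? |
|---|---|---|
| >0.2 mg/kg/day, discontinued in Part 1 | yes | no |
| >0.2 mg/kg/day, entered Part 2 | yes | yes |
| ≤0.2 mg/kg/day, discontinued in Part 1 | yes | no |
| ≤0.2 mg/kg/day, skipped Part 2 | yes | no |
| ≤0.2 mg/kg/day, entered Part 2 | yes | yes |
| No corticosteroid at Day 1, entered Part 2 | no | yes, unless filtered out |

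**Inputs (all assumed; the documents give none).** Among Day-1 users, *a* is the share at ≤0.2 mg/kg/day, *p1* the share passing Part 1 (taken equal in both dose groups), and *q* the share of higher-dose entrants to Part 2 who end at the threshold. For now, low-dose children are taken to meet the endpoint and discontinuers are classified by last dose.

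**Formulas**
- Day-1 percentage = a + (1 − a) × p1 × q
- OLPT2 percentage if low-dose children skip Part 2 = q
- OLPT2 percentage if every low-dose child who passes Part 1 enters Part 2 = a + (1 − a) × q

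**Results at p1 = 0.7, q = 0.6**

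| a | Day-1 | OLPT2, low-dose skip | OLPT2, none skip |
|---|---|---|---|
| 0.10 | 0.10 + 0.90 × 0.42 = 47.8% | 60.0% (+12.2) | 64.0% (+16.2) |
| 0.30 | 0.30 + 0.70 × 0.42 = 59.4% | 60.0% (+0.6) | 72.0% (+12.6) |
| 0.50 | 0.50 + 0.50 × 0.42 = 71.0% | 60.0% (−11.0) | 80.0% (+9.0) |

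If low-dose children skip, the sign changes at a = q(1 − p1)/(1 − p1·q) = 0.18/0.58 = 0.31. Over p1 from 0.6 to 0.8 and q from 0.4 to 0.8 that point runs from 0.12 to 0.62. With a from 0.1 to 0.5 the difference runs from +26.8 to −26.0 points. If none skip, the difference is (1 − a) × q × (1 − p1), which is +4.0 to +28.8 points over the same range.

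**Discontinuers counted as not achieved.** Let OLPT2 show 60%, and again take skippers as achieving.
- 30% discontinued in Part 1, 10% skip: 0.10 + 0.60 × 0.60 = 46%, so OLPT2 is 14 points too high.
- 10% discontinued in Part 1, 30% skip: 0.30 + 0.60 × 0.60 = 66%, so OLPT2 is 6 points too low.

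The direction stays open under this rule too.

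**Skippers need not meet the endpoint.** The skip rule is in mg/kg only, while the endpoint applies the lower of two limits. The limits coincide at 10/0.2 = 50 kg. A 60 kg child at 0.2 mg/kg/day takes 12 mg/day, may skip, and fails the endpoint. In the a = 0.50 row, the 11-point shortfall vanishes if 0.11/0.50 = 22% of low-dose users exceed 10 mg/day.

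**Taper success.** Let *t* be the success rate among required tapers who enter Part 2. OLPT2 reports t. Among all Day-1 users required to taper, the rate is p1 × t: at t = 0.8 and p1 of 0.6 to 0.8, 80% against 48% to 64%. Whether this is a discrepancy depends on what *applicable* means.

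**The case against.** For taper success the defence is good. The endpoint is limited to *applicable* children tapering per protocol. Doses are held stable in Part 1, Protocol Table 1 sets targets from the dose at the end of Part 1, and SAP Table 6 dates the start of Part 2 from the first taper day. OLPT2 is then a coherent at-risk set. Counting a Part 1 non-responder, who never attempted a taper, as a taper failure is a choice of estimand on which statisticians may differ. That stands.

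A reader might infer that both percentages fail the open-label objective on tapering. The documents do not support this: that objective does not mention the dose threshold, so the dose point rests on the endpoint wording. A reader might also infer that OLPT2 necessarily flatters the drug. That too goes further than the text. Skipping is permitted rather than required, optional tapering below the threshold exists (Protocol Table 2), and Protocol 3.2.1 sends some low-dose children to Part 2, so the sign depends on how many skip.

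The Table 4 rows name Part 2 and OLPT2 openly, which limits the risk of misreading. None of this answers the dose endpoint. Filtering OLPT2 to Day-1 users removes non-users but restores neither skippers nor Part 1 discontinuations. The general provision in SAP 6.2.2 for open-label overall summaries yields to specific instructions, and SAP 4.2 defines no overall set.

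**Conclusion.** For the dose endpoint the SAP contradicts itself on both population and time point, and the computed percentage would describe a different group from the one defined. That conclusion needs no assumption about size. The size and sign do: the illustrated gaps of +26.8 to −26.0 points rest on assumed shares, equal Part 1 pass rates, low-dose children skipping and meeting both dose limits, and classification by last dose. If no low-dose child skips, OLPT2 is too high throughout the range examined.

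Taper success is a missing definition, not an error. It would be tempting to call that percentage inflated, but that follows only if *applicable* means all Day-1 users required to taper, which the SAP does not say.

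Both endpoints are descriptive, no test depends on them, and the primary analysis is untouched. Severity is minor.

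**What to change.** **Dose endpoint (SAP 6.2.2 and Table 4).**
- Use OLPT1 subjects on corticosteroids at Day 1 as the denominator.
- Classify each by dose at the end of that child's own open-label phase, applying both the mg/kg and the mg/day limits, without presuming that skippers achieve it.
- State the rule for discontinuers, for example not achieved, with a second display by last open-label dose.
- Keep the OLPT2 percentage, limited to Day-1 users and labelled as among those entering Part 2.

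**Taper success (SAP 3.2.2).** Define *applicable*. If it means having entered Part 2, OLPT2 limited to Day-1 users stands and should be labelled as conditional on reaching Part 2. If it means Day-1 users required to taper, add that OLPT1-based percentage alongside.

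**Protocol.** Sections 3.2.1 and 3.2.2 must be reconciled on whether children not required to taper enter or skip Part 2.

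**Cost.** A few lines of SAP wording and one extra table from data already collected. The resulting percentage may be less favourable.
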